### **12.3 Records Retention**

It is the investigator's responsibility to retain study essential documents for a minimum period of 7 years following completion of the study per UW-Madison institutional policy, or at least 2 years after the last approval of a marketing application in their country and until there are no pending or contemplated marketing applications in their country or at least 2 years have elapsed since the formal discontinuation of clinical development of the investigational product, whichever comes last.

### **12.4 Retention for Future Research: Data & Biospecimen Banking**

#### **12.4.1 Purpose of Storage**

Samples, linked data (including only date, location and county of collection) and viral sequences will be stored for future research projects potentially related to saliva sample and viral sequencing techniques.

#### **12.4.2 Data and/or Biospecimens Being Stored**

Data and viral sequence will be retained and linked to the sample being stored.

#### **12.4.3 Location of Storage**

The samples will be stored at approx -80°C at AVRL or a designated departmental storage site on the UW campus for biospecimens of this nature.

#### **12.4.4 Duration of Storage**

The samples will be stored for the duration of the study or up to 7 years. Data associated with the samples and viral sequencing will be kept indefinitely.

#### **12.4.5 Access to Data or Biospecimens and Security Measures**

All members of the study team at the UW-Madison will have access to the consent forms, data, samples and viral sequences.

#### **12.4.6 Procedures to Release Data or Biospecimens**

Participants will consent to having their data (not their name) and viral sequences shared with the public via manuscripts, presentations and online databases therefore the study team will share that with other researchers when needed. Samples can be shared with UW researchers via the usual routes and non-UW researchers through the Material Transfer Agreement process.

#### **12.4.7 Process for Returning Results**

The study team will contact [name] and let him know the code of the samples that had a potential finding of clinical significance and he will use the key to contact the corresponding participant. If [name] has not received the key yet for the testing done that day, a member of the study team (that is not in a supervisory role to the participants) will give him the names and phone numbers of the individuals (or their parent/legal guardian) that had a potential finding of clinical significance over the phone. [name] will contact the participant with the results and reiterate that the test is investigational and the results are not diagnostic. He will strongly recommend that the participant obtain a clinical diagnostic test for COVID-19 and practice self-isolation until the results of the test are received. [name] will also provide information about testing options.

#### **12.4.8 Process for Tracking Subject Consent and Authorization**

The study team will create a spreadsheet to document which samples and data are allowed to be shared.

### **12.5 Protocol Deviations**

A protocol deviation is any noncompliance with the protocol. The noncompliance may be either on the part of the subject or the investigator. As a result of deviations, corrective actions may be implemented.

It is the responsibility of the Principal Investigator/study team to use continuous vigilance to identify and report deviations. The Principal Investigator is responsible for assessing whether the deviation constitutes noncompliance as defined by the reviewing IRB and if so, reporting it in accordance with posted guidance. The site investigator is responsible for knowing and adhering to the reviewing IRB requirements.

### **12.6 Publication and Data Sharing Policy**

This study will be conducted in accordance with the following publication and data sharing policies and regulations:

National Institutes of Health (NIH) Public Access Policy, which ensures that the public has access to the published results of NIH funded research. It requires scientists to submit final peer-reviewed journal manuscripts that arise from NIH funds to the digital archive PubMed Central (<https://www.ncbi.nlm.nih.gov/pmc/>) upon acceptance for publication.

This study will comply with the NIH Data Sharing Policy and Policy on the Dissemination of NIH-Funded Clinical Trial Information and the Clinical Trials Registration and Results Information Submission rule. As such, this trial will be registered at ClinicalTrials.gov, and results information from this trial will be submitted to ClinicalTrials.gov. In addition, every attempt will be made to publish results in peer-reviewed journals.

Data from this study may be requested from other researchers 7 years after the completion of the primary endpoint by contacting [name] at the University of Wisconsin - Madison.

## 13.0 STUDY ANALYSIS

### 13.1 Statistical Hypotheses

- **Primary Efficacy Endpoint(s):**

This is not a comparative study so there is not a formal, testable null hypothesis, per se. The purpose of the study is to determine if rapid, onsite testing for SARS-CoV-2 can be performed. Tests with potential findings of clinical significance using the RT-LAMP assay will be referred to clinicians for follow-up, but we are not privy to the results of follow-up diagnostic tests that participants may undertake in consultation with their healthcare provider.

### 13.2 Sample Size Justification

The key question of whether we can establish rapid, on-site testing and identify issues that would challenge scale-up and expansion to additional sites will benefit from testing as many individuals as possible. We anticipate that a single test site will initially be able to process up to 200 samples a day, growing to up to 1,000 samples a day as workflows are optimized and improved.

### 13.3 Subject Population(s) for Analysis

We will analyze data from all individuals who consent to receive RT-LAMP testing. All results will be used in analyses, unless they are excluded due to technical or quality control issues (e.g., samples are incorrectly pipetted or there is evidence of cross-contamination).

### 13.4 Statistical Methods

As noted above, our intention is to deploy and scale testing, so statistical methods aren't germane; there is no comparator group.

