Objective(s)	To show we can safely, consistently, and accurately detect high levels of SARS-CoV-2 RNA in non-invasive saliva samples using a mobile laboratory.
Endpoints	When we have tested at least 10000 samples and consistently shown that the assay can detect SARS-CoV-2 safely, consistently and accurately at multiple locations using the mobile laboratory and can be organized to test participants repeatedly over time.
Study Design	This is a non-randomized study where every participant will undergo the same procedure of spitting into a tube.
IND or IDE Number	Requesting an IDE nonsignificant risk (NSR) determination from the IRB.
Study Intervention	The RT-LAMP assay detects SARS-CoV-2 RNA in saliva samples using Salus Discovery LLC's RNA extraction technology.
Total Number of Subjects	A total of 10000 subjects could be recruited from the study sites.

Study Population	Anyone over the age of 5yrs old with consent to provide a saliva sample will be eligible to participate.
Estimated Subject Duration	The duration of the study for each subject is approximately 20 minutes each visit.
Estimated Enrollment Period & Study Duration	Study enrollment will occur over a 12 month period.

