## 5.0 INTRODUCTION

### 5.1 Disease Background

Virtually all COVID-19 RNA assays require centralized laboratories. Samples collected in locations including public testing sites, workplaces, nursing homes, and residential housing are transported to centralized laboratories for testing, leading to lengthy delays in results reporting. The window of maximal contagiousness is thought to be only a few days, so these delays create the risk of excess transmission. Current testing methods are painful, which encourages testing hesitancy. Rapid, onsite detection of SARS-CoV-2 RNA from non-invasive saliva could overcome these issues and provide a pathway to high-throughput detection of people at the greatest risk of SARS-CoV-2 transmission but the logistics of such a testing program require real-world prototyping. That is the purpose of this project.

Shown below are RT-LAMP results using residual specimens from known SARS-CoV-2+ cases. Each vertical series of points is a different sample, the datapoints for each sample indicate performance with a different primer set (a variable that we were optimizing in this experiment). You'll note that all of these samples were detected with our RT-LAMP assay. There was one sample that didn't perform well with every

primer set (the one with the least amount of virus, Ct ~ 30), but this sample had the lowest amount of input virus.

**False positives are rare to non-existent.** Early in our RT-LAMP testing, we received blinded samples from the State Lab of Hygiene. 15/15 SARS-CoV-2-negative samples were properly classified. 14/15 SARS-CoV-2+ samples were properly classified. This was an early embodiment of the technology and the one sample that was a false negative also had a Ct ~ 30, corresponding to the low end of what we reasonably expect to detect right now:

Sample ID	Approx Ct	Expected Result	RT-LAMP concordance with CDC assay
nCoV-1	21	SARS-CoV-2	
nCoV-2		Negative	
nCoV-3	20	SARS-CoV-2	
nCoV-4	27	SARS-CoV-2	
nCoV-5		Negative	
nCoV-6	20	SARS-CoV-2	
nCoV-7		Negative	
nCoV-8	28	SARS-CoV-2	
nCoV-9		Negative	
nCoV-10		Negative	
nCoV-11	21	SARS-CoV-2	
nCoV-12	29	SARS-CoV-2	
nCoV-13		Negative	
nCoV-14	22	SARS-CoV-2	
nCoV-15		Negative	
nCoV-16		Negative	
nCoV-17	23	SARS-CoV-2	
nCoV-18		Negative	
nCoV-19		Negative	
nCoV-20		Negative	
nCoV-21	26	SARS-CoV-2	
nCoV-22		Negative	
nCoV-23		Negative	
nCoV-24	23	SARS-CoV-2	
nCoV-25		Negative	
nCoV-26	24	SARS-CoV-2	
nCoV-27	23	SARS-CoV-2	
nCoV-28		Negative	
nCoV-29	20	SARS-CoV-2	

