nCoV-30	29	SARS-CoV-2	

Will this assay generate a lot of false positives? No. Could it generate some false negatives, especially for people who have low amounts of virus and are not thought to be contagious? Yes, and that is explicitly what we aim to learn as we bring this test into the “real-world”. Can a test that identifies people who are contagious be useful even if it isn’t as sensitive as a diagnostic test?

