## 6.0 STUDY OBJECTIVES AND ENDPOINTS

Objectives	Endpoints	
		Primary
To show we can safely, consistently, and accurately detect high levels of SARS-CoV-2 RNA in non-invasive saliva samples using a mobile laboratory.	When we have tested at least 10000 samples and consistently shown that the assay can detect SARS-CoV-2 safely, consistently and accurately at multiple locations using the mobile laboratory.	

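### The only primary endpoint claims accuracy, but the plan guarantees no reference result on any participant sample and plans no accuracy analysis; it should be restated as feasibility

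*Combined protocol and SAP*

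**What the plan says.** - **Endpoint.** Section 6.0 lists one objective and one endpoint. The endpoint is reached when at least 10,000 samples have been tested and the team has "consistently shown that the assay can detect SARS-CoV-2 safely, consistently and accurately at multiple locations using the mobile laboratory". The synopsis (3.1) adds repeat testing: "safely, consistently and accurately at multiple locations using the mobile laboratory and can be organized to test participants repeatedly over time". Neither gives a measure, a threshold or a reference standard.
- **False results.** Section 5.1 asks whether the assay could miss infections and answers "Yes, and that is explicitly what we aim to learn as we bring this test". On the other error it is firm: "False positives are rare to non-existent", and later "Will this assay generate a lot of false positives? No".
- **Earlier data.** Of residual specimens from known cases, used while primers were being optimised, 5.1 says "all of these samples were detected with our RT-LAMP assay". Of blinded samples tested with an early form of the assay it says "15/15 SARS-CoV-2-negative samples were properly classified. 14/15 SARS-CoV-2+ samples were properly classified".
- **Target.** Section 7.1 says the assay looks for high amounts of viral RNA and expects many PCR-positive samples to test negative.
- **Possible reference results.** Section 11.1 allows PCR, viral load or sequencing on any sample but does not say which or how many. Section 7.1 requires agreement to sequencing of any virus found. Section 13.1 says the study will not see the results of outside follow-up tests.
- **Run checks.** Section 11.2 has duplicate reactions, and two negative and two positive controls per batch.
- **Analysis.** Section 13.1 gives the purpose as finding out whether onsite testing can be done. Section 13.2 has no precision target. Section 13.3 lets technical and quality-control failures leave the analysis. Section 13.4 states "our intention is to deploy and scale testing, so statistical methods aren't germane; there is no comparator group".
- **End of study.** Section 7.2 asks for consistent detection at several locations and mentions neither accuracy nor 10,000 samples.

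**The concern.** The endpoint and the analysis section describe different studies. One promises to show accuracy; the other asks whether a mobile laboratory can be run. The reason given for planning no methods, that there is no comparator group, does not apply to accuracy. Sensitivity and specificity compare two results on the same sample, so a single-group study can estimate them if a reference result exists.

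Section 12.6 commits the study to reporting results on ClinicalTrials.gov. An endpoint that counts accuracy as shown once 10,000 samples have been processed would then be reported with no data behind that word. *Consistently* and *safely* have no measure either, so nobody can tell from the document when 7.2 has been met.

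**Working it through.** **1. The plan's own figures.** The table in 5.1 holds 15 positive and 15 negative samples, as the text says; 14/15 = 93.3% and 15/15 = 100%. The 10,000 cannot be re-derived, because no alpha, power, rate or precision is given. It is practicable: at the daily rates in 13.2, one site needs 10,000/200 = 50 days or 10,000/1,000 = 10 days, within the 12-month enrolment period.

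**2. Is any participant sample sure to get a reference result?**

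| Source | What the plan commits to | Can it show accuracy? |
|---|---|---|
| Outside diagnostic tests (13.1) | Results not obtained | No |
| In-study PCR or viral load (11.1) | Permitted; no selection rule, number or comparison | Only if done and compared |
| Sequencing of virus found (7.1) | Agreement required; no promise to sequence every positive | Could confirm some positives; cannot reveal missed ones |
| Batch controls and duplicates (11.2) | Every batch | Checks the run, not the classification of participants |

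The guaranteed number is 0 of 10,000.

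**3. Can the pilot stand in?** Exact (Clopper-Pearson) 95% limits:
- Positives, 14/15: lower limit is the 2.5% quantile of Beta(14, 2) = 68.1%; upper limit is 0.975^(1/15) = 99.8%.
- Negatives, 15/15: lower limit is 0.025^(1/15) = 78.2%; upper limit is 100%. A false-positive rate up to 100 − 78.2 = 21.8% is not excluded.

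To show what that leaves open, assume 10,000 samples, 1% prevalence and 93.3% sensitivity, which gives 93.3 true positives. Predictive value = true positives / (true positives + 9,900 × (1 − specificity)):
- specificity 99.9%: 93.3/(93.3 + 9.9) = 90%
- specificity 99%: 93.3/(93.3 + 99) = 49%
- specificity 78.2%: 93.3/(93.3 + 2,158) = 4%

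The pilot also used an early version, 11.2 allows the method to vary, and scoring was against any PCR positive rather than against high viral RNA.

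**4. Can 10,000 samples support a feasibility endpoint?** Assume a true 95% of samples give a valid, timely result. The half-width is 1.96 × √(0.95 × 0.05 × D / 10,000), with D = 1 + (m − 1) × ICC for m samples per person (10.1.2 allows unlimited repeats):
- independent samples, D = 1: 0.43 points
- m = 5, ICC 0.05, D = 1.2: 0.47 points
- m = 20, ICC 0.20, D = 4.8: 0.94 points

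This is ample. A rate per run has fewer units and is less precise; how much less depends on batch size, which the plan does not fix.

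**5. What would keeping the accuracy claim take?** Assume 10,000 samples, 1% high-level positives and 90% sensitivity: 90 detected and 10 missed.

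| Specificity | RT-LAMP positives | RT-LAMP negatives | 10% to 20% of negatives |
|---|---|---|---|
| 100% | 90 | 9,910 | 991 to 1,982 |
| 99% | 90 + 99 = 189 | 9,811 | 981 to 1,962 |
| 78.2% | 90 + 2,158 = 2,248 | 7,752 | 775 to 1,550 |

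The chance of finding no false negative is (1 − 0.01 × 0.1 × f)^10,000, which is 37% when a fraction f = 10% of negatives is verified and 14% when f = 20%. At 100% specificity, if none is found, up to 34 missed positives (at 10%) or 16 (at 20%) remain compatible with the data. Sensitivity could then be as low as 90/124 = 73% or 90/106 = 85%.

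**The case against.** The best defence is that this is openly a feasibility study. Sections 13.1, 13.2 and 13.4 say so, 5.1 gives real-world prototyping of the logistics as the purpose, and 7.2 leaves accuracy out. Participants are told that the test is not diagnostic, and negative results are not returned. All of this stands, and it points to the remedy: the stray element is the word in the objective and endpoint, not the design. It does not remove the contradiction, because the endpoint is what results are reported against.

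Several stronger readings are tempting, and the documents do not support them:
- *No reference testing is possible.* It is permitted by 11.1, and agreement to sequencing is required by 7.1. It is not guaranteed and not analysed.
- *The assay is inaccurate.* The pilot counts are good. They are too few to establish accuracy, and an upper limit of 21.8% is not an estimate of the false-positive rate.
- *The pilot shows how sensitivity depends on Ct.* The plan sets no formal cut-off for a high level, only benchmarks (10^6 copies per ml in 11.2, Ct about 30 in 5.1). Any split would be chosen with the miss already known.
- *A control arm or hypothesis test is needed.* Neither is.
- *Site is not recorded.* Section 12.1.1 omits it, but 3.1, 11.1 and 12.4.1 name site or location.
- *Only positive samples can be kept.* Step 10 of 11.2 mentions positives, but 7.1, 8.5, 11.1 and 12.4.1 allow banking generally.

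**Conclusion.** The point holds and should be fixed before results are reported. As written, the sole endpoint can be declared met, including its accuracy element, with a reference result on none of 10,000 samples, and no planned analysis could test the claim. The pilot does not rescue it: its lower 95% limits are 68.1% for positives and 78.2% for negatives.

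This conclusion rests on the text and on the pilot counts, not on assumed rates. The prevalence, sensitivity, specificity, ICC and validity rates used above are illustrative, since the documents give none. The verification figures treat samples as independent and so are best cases. The sample size is not shown to be wrong: 10,000 has no statistical derivation but is enough for feasibility proportions.

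**What to change.** 1. Remove *accurately* from the objective and endpoint in 3.1 and 6.0. Mark the false-negative aim in 5.1 as exploratory; it need not be deleted. State that sensitivity and specificity in participants will not be concluded.
2. Restate the objective, endpoint and 7.2 as feasibility of onsite testing. In 13.4 name the measures: valid-run and control-pass rate, duplicate concordance, turnaround time, samples per day by site, and count of unanticipated problems (defined in 15.1). Give 95% intervals that allow for repeat samples per person, and sponsor-set targets that decide when 7.2 is met.
3. Define a valid run, including what follows when a control fails, and count samples excluded under 13.3 in the denominator.
4. Add collection time and result time to 12.1.1, and align it with the site or location already named in 3.1, 11.1 and 12.4.1.

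The cost is a smaller claim, two time fields and a run log, with no added assays, visits or samples.

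Only if the sponsor keeps the accuracy claim: prespecify a reference comparison on the same saliva for all RT-LAMP positives and a random fraction of negatives, weighted by the inverse of that fraction, against a stated definition of a high level. This is not cheap. Under the assumptions in step 5 it takes about 990 to 1,980 negatives (at 100% specificity; fewer if specificity is lower) plus 90 to 2,248 positives, and the intervals stay wide when positives are few. Two passages would also have to be dealt with first. Section 7.1 makes agreement to molecular testing part of consent while 8.5 allows opting out, and these must be reconciled. Section 11.1 says molecular results are not relayed to participants, although verification would reveal missed positives.

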## 14.0 RISK/BENEFIT ASSESSMENT

### 14.1 Potential Benefits to the Subjects

There will be no direct health benefit to participants.

Conventional SARS-CoV-2 testing is uncomfortable and has a long lag time between testing and results reporting. The benefits to society are that if we can show that onsite testing is possible then more people can be tested, more conveniently, and with more rapid results dissemination than is possible today.

If more places such as assisted living residences, dorms and work places have access to this type of testing then more people who have COVID-19 are able to self-isolate and fewer people will come in contact with them and become infected themselves.

### 14.2 Known Potential Risks

There are no risks associated with sample collection. There could be some psychological stress associated with receiving a potential finding of clinical significance. Individuals with a potential finding of clinical

significance may be asked by medical professionals to self-isolate while diagnostic testing is performed and processed which could create additional psychological stress.

The consent documentation clarifies that the rapid COVID-19 test is experimental and not allowed to be used by a healthcare provider. The participants are encouraged to get a clinical diagnostic test to confirm any results of potential findings of clinical significance because we do not know yet if having that result means people are immune or protected from getting COVID-19 again. Additionally, a negative result does not mean that the participant does not have COVID-19 or the infection that causes it therefore they are being told to continue to adhere to local guidelines.

### **14.3 Risk/Benefit Analysis**

The benefit of getting this test and impacting the spread of COVID-19 outweighs the potential short-term stress associated with getting a result of a potential finding of clinical significance and talking to a physician with appropriate expertise about getting a diagnostic test.

## **15.0 DATA AND SAFETY MONITORING**

### **15.1 Unanticipated Problems**

An unanticipated problem (UP), as defined by the DHHS Office for Human Research Protection (OHRP), is any incident, experience, or outcome that meets all of the following criteria:

- The incidence, experience, or outcome is unexpected given the research procedures described in protocol-related documents (e.g., the study protocol, the informed consent documents) and the characteristics of the subject population being studied.
- An event may be considered unexpected if it exceeds the nature, severity, or frequency described in the study-related documents.
- The incidence, experience, or outcome is related or probably related to participation in the research study. "Probably related" means the incidence, experience, or outcome is more likely than not to be caused by the research study procedures.
- The occurrence of the incidence, experience, or outcome suggests that the research places subjects or others at a greater risk of harm (physical, psychological, economic, or social) than was previously known or recognized.

The investigator will report UPs to the reviewing IRB. The UP report will include the following information:

- Protocol identifying information: protocol title and number, PI's name, and the IRB project number;
- A detailed description of the event, incident, experience, or outcome;
- An explanation of the basis for determining that the event, incident, experience, or outcome represents an UP;
- A description of any changes to the protocol, informed consent documents, or other corrective actions that have been taken or are proposed in response to the UP.

UPs will be reported within 14 days in accordance with posted guidance.

